Hypothesis: IM epinephrine is an efficacious adjunct to inhaled bronchodilators (β_2 agonists) for children with severe asthma exacerbation.

Methods:

Study design: This is a repeated measures, parallel group, single-blinded randomized controlled therapeutic trial.

Study site: Kosair Children's Hospital emergency department

Eligible participants: The study population will be comprised of children age 6-17 years old who present to the ED with severe status asthmaticus as diagnosed by the treating provider and verified by peak expiratory flow rate (PEFR) of <60% of predicted prior to intervention or a clinical asthma score of 7 or greater.

Inclusion criteria

- 1. Age greater than 6 years and less than 18 years
- 2. Pre-existing diagnosis of asthma
- 3. Presenting to the ED with an asthma exacerbation

Exclusion criteria

- 1. History of chronic lung or upper airway disease other than asthma
- 2. History significant, uncorrected congenital heart disease or cardiac arrhythmia
- 3. History of thyroid disease, stroke, sickle cell disease, or renal disease
- 4. Systolic blood pressure greater than the 95th percentile for height, age, and gender
- 5. Impending respiratory failure
- 6. Allergy to epinephrine
- 7. Pregnancy
- 8. Weight < 20 kg

Screening procedures: Patients presenting to the ED for asthma exacerbation who meet the inclusion criteria will be considered for enrollment in the study. A brief form will be completed by a study investigator or research assistant to assess for eligibility.

To accurately ascertain predicted PEFR, height will be measured. PEFR testing will be performed by respiratory therapists (RT) in the ED once the patient is brought into a treatment room. The RT will also measure the clinical asthma score.

Girls who meet all of the other screening criteria will be asked if they have achieved menarche. If so, they will be asked to give a urine sample so that a pregnancy test can be performed.

Consent procedures: The study will be described in detail initially. If the parents and patient would like to participate, then a research member will discuss the informed consent and assent (if applicable) with the families and obtain signatures.

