Allocation concealment: The RT will be blinded as to whether the subject receives a dose of IM epinephrine. Once a patient is determined to be eligible for the study, the research team will complete informed consent/assent. A pharmacy generated randomization schedule will be utilized and sealed envelopes with the allocations (treatment or control) will be kept in the charge nurse's office.

At the time of allocation, the charge nurse will instruct all staff to leave the subject's room. The charge nurse will then open the designated envelope and personally prepare and administer IM epinephrine if the subject is allocated to the treatment arm. If the subject is allocated to the control arm, the charge nurse will draw up a syringe with the appropriate amount of saline as if an injection of epinephrine was going to be given to the participant. The charge nurse will take this syringe into the subject's room, but not administer it. Instead, a 'sham' Band-Aid will be placed over the thigh of the subject. They will be instructed not to reveal to the RT, research team, or bedside nurse whether or not an injection was actually given. Participants and families will be similarly instructed. The RT will remain blinded throughout and will be responsible for measuring all PEFRs and CASs.

Having block sizes that are randomly determined, as well as having larger block sizes of 8-12 will help minimize a member of the research team or the RT guessing the allocation of the next participant and potentially biasing recruitment or assessment. To further assess blinding, at the conclusion of the study, we will ask the RTs to guess which group the subjects they assessed were in.

Study data: The following data will be measured at time points (t_{15} , t_{30} , t_{60} , t_{90} , and t_{120}) minutes following IM epinephrine or sham drug administration: PEFR (if able), CAS, heart rate, respiratory rate, and pulse oximetry. This data will also be recorded at the time of discharge or admission from the ED. Also recorded will be amount and timing of bronchodilator, anticholinergic, and corticosteroid therapy given. Additionally, any other therapies and interventions will be recorded (i.e. oxygen administration, assisted ventilation, magnesium sulfate administration, etc.). ED length of stay as well as disposition will be noted.

Primary outcome measure: Change in percent of predicted PEFR/CAS 15 minutes after the study intervention (t_{15}).

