Secondary outcome measures:

1. Change in percent of predicted PEFR/CAS at t₁₅

- 2. Disposition
- 3. Change in percent of predicted PEFR/CAS at t₃₀, t₆₀, t₉₀ and t₁₂₀
- 4. Change in percent of predicted PEFR/CAS at t₃₀, t₆₀, t₉₀ and t₁₂₀
- 5. Change in respiratory rate at t_{15} , t_{30} , t_{60} , t_{90} and t_{120}
- 6. Change in heart rate at t_{15} , t_{30} , t_{60} , t_{90} and t_{120}
- 7. Need for supplemental oxygen at t_{60} , t_{90} and t_{120} (defined as a room air pulse oximetry of <93%)
- 8. Need for albuterol at t_{60} , t_{90} and t_{120}
- 9. Number of hours of albuterol therapy
- 10. ED length of stay

Statistical analysis plan: First straightforward tests for differences among the two groups of individuals will be performed. Analysis of Variance (ANOVA) techniques will be used to test for differences among continuous variables, while Kruskal-Wallis, Fischer's Exact Tests and Wilcoxon methods will be used to test for differences among categorical variables. To examine the outcomes of: (1) change in percent of predicted PEFR/CAS, (2) respiratory rate, (3) heart rate, (4) hours of albuterol therapy and (5) length of stay in the ED, separate mixed-effects general linear models will be developed for each outcome (five models will be developed). The two arms (IM epinephrine and no epinephrine) will be analyzed as fixed effects, and time (time since randomization) will be analyzed as a repeated measures effect. Traditional risk factors (e.g. age, gender, and ethnicity) will be incorporated as covariates during secondary analyses. All main effects and all two-way interaction effects will be investigated for significance from the mixed-effects models developed. Negative binomial regression and logistic regression techniques will also be used to evaluate (7) need for supplemental oxygen and (8) need for albuterol. Life table analysis and Kaplan-Meier techniques will initially be used to analyze the time-related variables (e.g., time to discharge). The Log-rank test will be used to test for differences among survival curves. In addition, Cox (proportional hazards) regression techniques will be developed to test for differences among groups as well as allow for adjustment for additional covariates and risk factors. Cox regression will allow us to investigate all potential main effects and interaction effects. All statistical analyses will be performed by a statistician who is blinded to the treatment allocation of the two groups.

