Planned interim analysis: Interim analyses, reported to the data monitor will be performed at 6, 9 and 12 months after the first participant is randomized. A Lan-DeMets spending function approach will be used to monitor the need for early trial termination.

Power calculation: We will develop separate mixed-effects general linear models for each of the outcomes. For a sample size (n=54) the study has 81% power to detect a 12% main effect of each treatment for each outcome. The estimated power for detecting a 5% interaction effect is 32%. The total sample size required to achieve 80% power to detect an interaction effect, based on the full-factorial designed proposed, is n=1728; which is not a feasible number in which to recruit and enroll. In addition, we will develop Cox proportional hazards regression models to assess the association between group assignment and time related outcomes. For the anticipated sample size (n=54), this study has 80% power to detect a hazards ratio of 1.82 with two-sided α =0.05. Lastly, multiple logistic regression techniques will be utilized to assess

the association between group assignment and dichotomized outcomes. Using the dichotomized version of some outcomes, this study has 80% power to detect on odds ratio of 1.58 with a two sided α =0.05 (n=54). Therefore, we have more than sufficient numbers of participants in each comparison group.

We anticipate that less than 10% of all potential participants will drop out. Therefore, we will recruit a total of 60 individuals for the current study (n=30 per group). This is a feasible sample size for the research team to recruit and enroll in the current study. Power calculations were based on the anticipated total sample size (n=54) that will be available for complete analysis. Using a block randomization scheme (with random block sizes of 8-12), we anticipate that n=30 participants will be assigned to each group.

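### Secondary outcomes are tested and powered in the same way as the 15-minute primary, with no rule to stop a chance secondary result from standing in for a null primary

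*Combined protocol and SAP*

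**What the plan says.** Under Primary outcome measure, the protocol names one outcome: "Change in percent of predicted PEFR/CAS 15 minutes after the study intervention". Secondary outcome measures then lists ten items. Item 1, "Change in percent of predicted PEFR/CAS at t₁₅", repeats the primary. Items 3 and 4 are identical: "Change in percent of predicted PEFR/CAS at t₃₀, t₆₀, t₉₀ and t₁₂₀". The rest are disposition, respiratory rate and heart rate at five times each, need for oxygen and need for albuterol at three times each, hours of albuterol, and ED length of stay.

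The Statistical analysis plan makes no distinction between the two tiers. It begins: "First straightforward tests for differences among the two groups of individuals will be performed". For five outcomes, with PEFR/CAS simply the first in the list, "separate mixed-effects general linear models will be developed for each outcome (five models will be developed". Every main effect and two-way interaction in those models is to be examined for significance. Logistic, negative binomial, log-rank and Cox analyses are added.

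The Power calculation states: "For a sample size (n=54) the study has 81% power to detect a 12% main effect of each treatment for each outcome". It adds 80% power at two-sided 0.05 for a hazard ratio of 1.82 and, for some dichotomized outcomes, an odds ratio of 1.58. It closes: "Therefore, we have more than sufficient numbers of participants in each comparison group".

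The Hypothesis, that "IM epinephrine is an efficacious adjunct to inhaled bronchodilators", names no outcome. The only error control in the document is the Lan-DeMets function under Planned interim analysis. That covers repeated looks over time, not several outcomes.

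**The concern.** Naming a primary outcome helps only if the plan also says what the other results can and cannot show. Here the secondaries get the same significance testing and a power claim of their own, and nothing says what follows if the 15-minute result is null and a secondary is not. A nominally significant respiratory rate or disposition result could then be presented as a planned, adequately powered test supporting the efficacy hypothesis. With this many outcomes, such a result can easily arise by chance.

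**Working it through.** **1. The plan's own power figures.**

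- *12% main effect, 81% power, 27 per arm.* No SD or alpha is stated. At two-sided 0.05, SD = 12 / [(1.960 + 0.878) × √(2/27)] = about 15.5 points. The figure is possible but cannot be reproduced from the document.
- *Hazard ratio 1.82, 80% power.* Events needed = 4 × (1.960 + 0.842)² / (ln 1.82)² = 31.4 / 0.359 = about 88. If all 54 children had the event, power = Φ(0.599 × √54 / 2 − 1.96) = Φ(0.24) = about 59%.
- *Odds ratio 1.58, 80% power, n=54.* With an assumed control rate of 40%, the treated odds are 0.667 × 1.58 = 1.053, a rate of 51.3%. The standard error is √[(0.240 + 0.250)/27] = 0.135. Power = Φ(0.113/0.135 − 1.96) = about 13%. Over control rates of 10% to 70%, power is about 8% to 13%.

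**2. How many secondary tests.** The plan gives no number. Two counts bracket the plausible readings. Both leave out the repeats (items 1 and 4) and heart rate, which the drug is expected to change.

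- One test per outcome: PEFR, CAS, respiratory rate, oxygen, albuterol need, disposition, albuterol hours, length of stay = 8. Counting PEFR/CAS as one and adding heart rate also gives 8.
- One test per listed time point: 4 + 4 + 5 + 3 + 3 + 1 + 1 + 1 = 22. Counting PEFR/CAS as one and including heart rate gives 4 + 5 + 5 + 3 + 3 + 3 = 23.

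**3. Chance of a false signal when the drug has no effect.** Each test is taken at two-sided 0.05. With independent tests the results are exact:

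- at least one secondary p<0.05, either direction: 1 − 0.95⁸ = 34%; 1 − 0.95²² = 68%
- null primary and at least one secondary significant for benefit: 0.95 × (1 − 0.975⁸) = 17%; 0.95 × (1 − 0.975²²) = 41%

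For correlated tests, standard-normal test statistics with a common correlation were simulated, the primary included for the second event.

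| Assumed correlation | 8 tests: any p<0.05 | 22 tests: any p<0.05 | 8 tests: null primary, false benefit | 22 tests: null primary, false benefit |
|---|---|---|---|---|
| 0 | 34% | 68% | 17% | 41% |
| 0.5 | 25% | 44% | 11% | 20% |
| 0.9 | 12% | 16% | 4% | 6% |

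A block structure for the 22 tests (0.8 within an outcome over time, 0.5 between outcomes) gives 39% for any p<0.05 and about 17% for a null primary with a false benefit.

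**The case against.** The plan does have a hierarchy of a kind: one outcome is labelled primary and the rest secondary. Unadjusted secondaries do not raise the primary test's error, and the harm needs a later reporting choice that the document does not announce. All of that stands. It limits the problem to over-reading of secondary p-values, but it does not supply the missing rule.

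A reader might infer stronger things that the document does not support:

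- *That every time point is tested and powered like the primary.* The plan specifies one mixed model per continuous outcome, and the 81% refers to a main effect in such a model. No separate test at each time is prescribed, the mixed models have no stated alpha, and the odds-ratio power covers only some outcomes. The 8-test count is therefore closer to the text; 22 is the upper reading.
- *That the false-signal rate is 44%.* That figure needs 22 tests and a correlation of 0.5, and no correlation is given anywhere. It also counts harm as well as benefit, whatever the primary shows. The event that matters is 11% to 20% at that correlation.
- *That the plan declares numbers sufficient for every comparison.* The closing sentence of the Power calculation is about participants in each comparison group, most naturally the two arms.
- *That the general wording of the Hypothesis licenses a claim on any outcome.* It is a statement of aim. It fails to tie the claim to the primary, but goes no further.

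The 5% size is also generous for categorical outcomes if Fisher's exact test is used, because that test is conservative at 27 per arm. Assuming a true size of 2% for the seven categorical tests lowers the block figure from 39% to 33%. Logistic regression is planned too, so this relief is partial. Against that, length of stay can be analysed by several methods and interactions are tested as well, so 22 is not a ceiling.

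**Conclusion.** The point holds as a gap in the rules for interpretation, not as inflation of the primary's error. The analysis and power sections treat primary and secondary outcomes alike, and nothing orders, adjusts or labels the secondary tests. Under no effect, the chance of at least one nominally significant secondary is about 12% to 34% on the per-outcome reading and 16% to 68% on the per-time-point reading. The chance of a null primary with a falsely beneficial secondary is about 4% to 17%, or 6% to 41%. These ranges rest on assumed correlations from 0.9 to 0, on the counts of 8 and 22, and on every test having its full 5% size. At the high-correlation end the second event is rare, so no single figure should be quoted as the trial's error rate. Separately, the odds-ratio power claim for secondary outcomes fails on any control rate tried, and the hazard-ratio claim needs more events than there are children in the analysis.

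**What to change.** In the Statistical analysis plan:

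- State first whether PEFR/CAS at 15 minutes is one comparison or two and, if two, how they combine into one decision.
- State that efficacy is judged on that primary comparison alone.
- State that all secondary outcomes, time points and interactions are exploratory, are reported as arm differences with 95% confidence intervals, and cannot establish efficacy if the primary is not significant.
- If a formal secondary claim is wanted, name a short fixed sequence, each step tested at two-sided 0.05 only after the primary and the preceding step succeed.

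In the Power calculation, limit the claim to the primary, and withdraw or correct the figures for secondary outcomes. With 27 per arm, an odds ratio of 1.58 has about 8% to 13% power, not 80%.

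The cost is a few sentences, with no added patients, data or procedures. The downside is that a secondary result with p<0.05 can no longer be presented as confirmatory, outside any sequence named in advance.

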Baseline data: Once screened, consented, and enrolled, the following demographic data will be collected: birthdate, gender, race, time of arrival to the ED, details of any treatment by a referring provider, symptom type and duration (hours), time since last inhaled bronchodilator (minutes), time since systemic corticosteroids (minutes), number and type of inhaled bronchodilator treatments in the preceding 24 hours, all home medications, drug and food allergies, past medical history, number of hospital admissions for asthma over the prior 12 months, and number of ICU admissions over the child's lifetime. Initial temperature, respiratory rate, heart rate, blood pressure, and pulse oximetry will be recorded. Finally, height, PEFR, and CAS will be measured by the respiratory therapist (RT) immediately prior to the study intervention. Additionally, the subject's family will be asked to complete an Asthma Control Tool (ACT). The ACT is a measure of how well the participant's asthma has been controlled over the preceding three months.

Intervention: Subjects will then be randomly assigned (50% chance) to receive a weight based dose of IM epinephrine 1:1000 or no adjunctive medication. The dose will be 0.2 mg for subjects 20-30 kg and 0.3 mg for subjects greater than 30 kg. This will be injected intramuscularly by an ED nurse into the anterior thigh muscles of the subject using a 1 ml syringe and a 23 gauge one inch needle.

In addition to the study intervention, the standardized treatment pathway based on the current asthma guidelines in use at our center will be utilized. This pathway includes nebulized albuterol, ipratropium bromide, and systemic corticosteroids. The duration and dosages of these other interventions will be administered at the discretion of the treating provider.

Randomization: A block randomization scheme will be used to promote balance at the end of the study. Block randomization ensures that after each block of individuals are enrolled in the study (n individuals in total); an equal number of individuals will be assigned to each group (n/2 individuals in each group). We will use random block sizes of 8-12.

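### The outcome list defines respiratory rate and heart rate as changes, the list of modelled outcomes does not, and the main models leave out the baseline reading

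*Combined protocol and SAP*

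**What the plan says.** The list of secondary outcome measures has, as item 5, "Change in respiratory rate at" 15, 30, 60, 90 and 120 minutes and, as item 6, "Change in heart rate at" the same five times.

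The statistical analysis plan assigns five outcomes to separate mixed-effects models: "1) change in percent of predicted PEFR/CAS, (2) respiratory rate, (3) heart rate, (4) hours of albuterol therapy and (5) length of stay in the" emergency department. Arm is a fixed effect, and "time (time since randomization) will be analyzed as a repeated measures effect". On interactions: "All main effects and all two-way interaction effects will be investigated for significance from the mixed-effects models developed". On covariates: "Traditional risk factors (e.g. age, gender, and ethnicity) will be incorporated as covariates during secondary analyses".

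The baseline data section says "Initial temperature, respiratory rate, heart rate, blood pressure, and pulse oximetry will be recorded". Height, peak flow (PEFR) and the clinical asthma score (CAS) are tied to the moment just before the study intervention. The vital signs are not. The study data section lists the five follow-up times and the time of discharge or admission, all after the intervention.

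**The concern.** The two lists do not describe respiratory rate and heart rate in the same way, and the plan never says how the initial readings are used. They could be subtracted, entered as a first time point, entered as a covariate, or ignored. Each choice is a different analysis, and the choice could be made after the data are seen.

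Respiratory rate bears on efficacy, and heart rate is the only cardiovascular measure among the listed outcomes of an epinephrine trial. With 54 analysable children aged 6 to 17, chance differences between arms at baseline will not be negligible. An analysis that does not use baseline well gives up precision that the trial has already paid for in data collection.

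**Working it through.** **The plan's own figure.** The power calculation states 81% power at n=54 for a 12% main effect on each outcome. It gives no SD, no correlation and no alpha for this model. With 27 per arm and an assumed two-sided alpha of 0.05, 81% power needs a standardised effect of (1.960 + 0.878) × √(2/27) = 0.772. That implies an SD of 12/0.772 = 15.5 if 12% means 12 units. The figure can be neither reproduced nor refuted, and it does not distinguish raw values from change.

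**Inputs.** 27 per arm (54 analysable, 1:1 randomisation). Rho, the correlation between baseline and follow-up, is not given; 0.3, 0.5 and 0.7 are assumed. SDs at baseline and follow-up are assumed equal and set to 1.

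**Step 1: the target.** Randomisation makes the expected baseline difference zero, so raw values and change scores have the same expected arm difference. Simulation (20,000 trials at each rho, true effect 0.772) gave mean differences of 0.771–0.774 for raw values and 0.768–0.774 for change.

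**Step 2: one trial.** The chance baseline difference d between arms has SD √(2/27) = 0.27 SD. The raw-value estimate carries rho × d on average, and the change estimate carries −(1 − rho) × d. The gap between them is rho × d + (1 − rho) × d = d. If the heart-rate SD were 20 beats/min (assumed), d has SD 20 × 0.272 = 5.4 beats/min. An imbalance of that size shifts the estimates as follows.

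| rho | raw (beats/min) | change (beats/min) |
|---|---|---|
| 0.3 | +1.6 | −3.8 |
| 0.5 | +2.7 | −2.7 |
| 0.7 | +3.8 | −1.6 |

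Conditional on the imbalance, baseline adjustment carries neither shift.

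**Step 3: precision at one time point.** Relative standard errors are 1 for raw values, √(2(1 − rho)) for change and √(1 − rho²) for baseline-adjusted values. Power is at the 0.772 effect.

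| rho | SE raw | SE change | SE adjusted | Power raw | Power change | Power adjusted |
|---|---|---|---|---|---|---|
| 0.3 | 1.00 | 1.18 | 0.95 | 81% | 67% | 85% |
| 0.5 | 1.00 | 1.00 | 0.87 | 81% | 81% | 91% |
| 0.7 | 1.00 | 0.77 | 0.71 | 81% | 96% | 98% |

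Against raw values, adjustment lowers the standard error by about 5%, 13% and 29%. Against change scores the ratio is √((1 + rho)/2), a fall of about 19%, 13% and 8%.

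**Step 4: five repeated readings.** With the same correlation rho between all readings (assumed), the mean of the five follow-up values has variance (1 + 4rho)/5 for raw values, that plus 1 − 2rho for change, and that minus rho² when adjusted.

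| rho | raw | change | adjusted |
|---|---|---|---|
| 0.3 | 0.44 | 0.84 | 0.35 |
| 0.5 | 0.60 | 0.60 | 0.35 |
| 0.7 | 0.76 | 0.36 | 0.27 |

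Raw and change still cross at 0.5, and adjustment has the smallest variance in each row.

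**Step 5: an open choice.** With no true effect, at least one of the raw-value and change-score tests at a single time point is significant in about 9% of simulated trials for rho from 0.3 to 0.8, against a nominal 5%.

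**Step 6: the interaction clause.** An arm-by-time term in a raw-value model is a difference in change from baseline only if the baseline reading is one of the time points. The plan does not say that it is. If it were, the arm main effect would average in a pre-treatment reading and be diluted.

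**Step 7: why the covariate reconciles the lists.** If change = a + b × arm + c × baseline, adding baseline to both sides gives value = a + b × arm + (c + 1) × baseline. The arm coefficient b is the same under either wording.

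**The case against.** The strongest reply is that the list of modelled outcomes is shorthand. It follows directly on the outcome list, drops the time points, and a little later reuses the secondary-outcome numbers 7 and 8 for oxygen and albuterol, so it may take its definitions from there. That is possible. A reader might infer that the plan commits to raw values, but it never says so. Even on the shorthand reading, the use of baseline stays unstated.

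A reader might also infer that raw-value models would fail to estimate the stated outcomes. They would not: step 1 shows the same expected arm difference. Nor does a chance imbalance pass in full into a raw-value estimate; about rho times it does, and change scores carry imbalance too, in the other direction. Nor is a loss of power against change scores established. It needs rho above 0.5. Below that, switching to unadjusted change scores would cost power.

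The covariate list is open-ended and names age, so part of the between-child spread may be dealt with, but only in secondary analyses. The figures rest on simple variance formulas rather than the exact planned model, whose covariance structure the plan does not give. These objections stand and limit the point to one of specification and efficiency. None of them argues against baseline adjustment.

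**Conclusion.** The point holds as a matter of clarity and efficiency. The two lists word respiratory rate and heart rate differently, and the main models do not include the baseline reading. The documents do not show a biased analysis or a certain loss of power.

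The gain from baseline adjustment depends on a rho that the documents do not give. It also assumes equal SDs over time, 27 per arm, and a baseline reading taken close enough to the intervention to be informative. If rho were near zero, the gain would vanish and the lost degree of freedom would be a very small cost. Only secondary outcomes are affected. Severity is low; this is a nearly free improvement.

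**What to change.** In the statistical analysis plan:

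- Name the second and third modelled outcomes as change in respiratory rate and change in heart rate, to match the secondary outcome list.
- Specify the main model for each as arm, time, arm-by-time and the child's own pre-intervention reading of that vital sign as a covariate.
- Report the arm difference, with its confidence interval, at each of 15, 30, 60, 90 and 120 minutes.
- State which pre-intervention reading is the baseline, since the baseline data section calls these vital signs only initial and does not place them relative to the intervention.

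The cost is a sentence or two of text and one degree of freedom in each of two models. An initial reading of both vital signs is already collected. If the sponsor prefers a reading taken just before the intervention, it could be recorded along with the PEFR and CAS already measured then.

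### The primary outcome is change at 15 minutes, but the analysis plan does not say which test decides it, and the stated 81% power cannot be tied to that time point

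*Combined protocol and SAP*

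**What the plan says.** - **Primary outcome measure:** "Change in percent of predicted PEFR/CAS 15 minutes after the study intervention".
- **Study data:** at 15, 30, 60, 90 and 120 minutes the trial records "PEFR (if able), CAS, heart rate, respiratory rate, and pulse oximetry". The same data are recorded at discharge or admission.
- **Secondary outcome measures:** item 1 is "Change in percent of predicted PEFR/CAS at t₁₅", which repeats the primary outcome. Items 3 and 4 are identical to each other and cover t30 to t120.
- **Statistical analysis plan:** it opens with "First straightforward tests for differences among the two groups of individuals will be performed", using ANOVA for continuous variables, with no outcome or visit named. PEFR/CAS change then gets one mixed model, in which the arms "will be analyzed as fixed effects, and time (time since randomization) will be analyzed as a repeated measures effect". All main effects and two-way interactions are to be examined. Age, gender and ethnicity "will be incorporated as covariates during secondary analyses".
- **Power calculation:** "For a sample size (n=54) the study has 81% power to detect a 12% main effect of each treatment for each outcome". The sample size for an interaction is "based on the full-factorial designed proposed".
- **Planned interim analysis:** three looks, at 6, 9 and 12 months, with Lan-DeMets spending.

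**The concern.** The primary question concerns an early effect at a single time. The model assigned to the primary variable covers two hours, and its arm effect, as usually fitted and reported, is an average over visits. Run that way, the plan answers a different question, with most of the weight on visits it calls secondary.

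At least three results could be presented as the primary one: the ANOVA at t15, the arm effect from the mixed model, and a t15 contrast from a model with arm-by-time terms. Labelling the covariate models secondary gives some order, but does not choose among these three. PEFR/CAS is also two measures, and PEFR is taken only when the child can perform it, so the scale is open too.

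At stake are the meaning of the primary result, control of the 5% error rate if the choice is made after seeing data, and the sample size justification. The interim boundaries are affected as well, because a spending function has to be applied to a designated test statistic.

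**Working it through.** **Inputs from the documents.** 54 children analysed (27 per arm), a 12% effect, 81% power, five scheduled post-dose visits.

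**Assumptions, because the documents give no values.** Two-sided 0.05 (stated only for the Cox and logistic calculations); 12% read as 12 points of percent-predicted PEFR; one scale; complete data; no interim looks; equal visit weights; compound symmetry of the post-dose changes with correlation ρ from 0.5 to 0.8.

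**1. The plan's own figure.** For a two-sample t test with 52 df the noncentrality is 12 / (SD × √(2/27)). Power of 81% requires SD = 15.25 (12 / 4.15 = 2.89). That SD is not in the documents, so the 81% can be neither reproduced nor refuted. For the same 12 points, power is 95% at SD 12, 82% at SD 15, 67% at SD 18 and 58% at SD 20.

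**2. Averaged effect against t15.** Let f = √((1 + 4ρ)/5). This is the ratio of the SD of a five-visit mean to the SD of one visit, and also the correlation between the two test statistics. In the mean, t15 has weight 1/5 and the secondary visits 4/5. If the mean effect over t30 to t120 is k times the t15 effect, the averaged effect is (1 + 4k)/5 of it. The two tests break even at (1 + 4k)/5 = f, whatever the SD.

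**3. Either test allowed to carry the claim.** Type I error is the chance that at least one of two standard normal statistics with correlation f exceeds 1.96 in absolute value.

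| ρ | f | Break-even k | Type I error, either test | Averaged-test power at k = 1 / 0.75 / 0.5 |
|---|---|---|---|---|
| 0.5 | 0.775 | 0.718 | 8.0% | 96% / 83% / 59% |
| 0.7 | 0.872 | 0.840 | 7.3% | 90% / 74% / 50% |
| 0.8 | 0.917 | 0.896 | 6.9% | 87% / 70% / 46% |

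The last column takes 15.25 as the single-visit SD, so the unadjusted t15 test has 81% power throughout.

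**4. If the 81% refers to the five-visit average.** The single-visit SD is then 15.25/f = 19.68, 17.49 or 16.64, and unadjusted t15 power for 12 points is 59%, 70% or 74%.

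**5. Baseline-adjusted t15 test.** With equal variances and baseline-to-t15 correlation r, adjustment multiplies the SD of change by √((1 + r)/2), which is 0.806 at r = 0.3 and 0.922 at r = 0.7.

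| What the 81% refers to | Adjusted SD, r = 0.3 / 0.7 | Power, r = 0.3 / 0.7 |
|---|---|---|
| Unadjusted t15 | 12.29 / 14.06 | 94% / 87% |
| Five-visit average, ρ = 0.5 | 15.87 / 18.15 | 78% / 66% |
| Five-visit average, ρ = 0.8 | 13.41 / 15.34 | 90% / 80% |

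**The case against.** The strongest reply is that the plan already contains a t15 test. The primary outcome is one number per child, and the opening ANOVA applied to it is a two-group comparison at t15. The mixed model need not average either. Once arm-by-time is included, the arm coefficient depends on coding: with t15 as the reference visit it is the t15 effect, and with continuous time it is the effect at time zero. This stands. A reader might infer that no planned test can address t15, and the text does not support that. What remains is that a t15 test is permitted but not designated.

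Three other strong readings also go too far.

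- **That the trial's type I error is 7% to 8%.** That rate needs a rule letting either test carry the claim. The plan states no such rule, and it does name t15 as primary.
- **That the 81% is wrong.** Its inputs are missing, so it is only unverifiable. Length of stay and hours of albuterol have one value per child, so for them the phrase can only mean a difference between arms. That plain meaning could hold for t15 too.
- **That the factorial wording contradicts the parallel-group design.** It sits in the sentence on interactions and may mean an arm-by-time layout.

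The equal 1/5 weights are also a simplification, since a further record is taken at discharge or admission. The repeated items in the secondary list may be a drafting slip between the two scales.

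**Conclusion.** The concern holds as a failure to identify the primary test. The outcome section fixes t15. The analysis section offers several routes and chooses none, and the ordinary reading of the one model assigned to PEFR/CAS gives four fifths of the weight to secondary visits. This rests on the text alone and needs no assumed number.

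The figures show why the choice matters and are conditional on the assumptions listed in the working. The averaged test has less power than the t15 test once the mean later effect falls below 72% (ρ = 0.5) to 90% (ρ = 0.8) of the t15 effect, and more power above that. The documents give no time course, so the direction for this trial is unknown. For the same reason, power for the t15 question cannot be read from the protocol and could lie on either side of 80%.

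**What to change.** Before any unblinded comparison, including the first interim look:

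- Name one primary test on one scale, PEFR or CAS, chosen in advance by the sponsor: the t15 arm contrast from a mixed model of change with categorical time, arm-by-time terms and the baseline value as covariate. Test it at overall two-sided 0.05 under the planned Lan-DeMets spending.
- Label as secondary the averaged arm effect, the t30 to t120 contrasts, the interaction tests and the other scale. Remove t15 change on the primary scale from the secondary list.
- Restate power for that contrast, giving the SD and its source.

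**Cost.** A few sentences and one power calculation. Baseline PEFR and CAS are already collected, and the fix requires no extra enrolment. There is a real trade-off: if the effect is constant over time, an unadjusted t15 contrast has less power than the average (81% against 87% to 96%). For the recommended adjusted test, with r from 0.3 to 0.7, power is about 87% to 94% if the 81% refers to unadjusted t15, and about 66% to 90% if it refers to the five-visit average. If the restated figure falls below 80%, it should be reported as such.
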